For safety reasons, a gradual dose escalation regimen will be implemented for mild AD dementia subjects receiving Siponimod/Placebo. The medication will be administered in 0.25 mg increments biweekly reaching the maximum dose of 1 mg. As a precaution, the initial higher doses will be given in a clinical setting, with subjects observed for six hours by study staff who are blinded to the study drug. This allows for prompt intervention in case of any distress, such as issues with heart or blood pressure. During these in-person visits, blood samples will be collected to monitor for signs of toxicity changes. Tests will include a complete blood count with differential, comprehensive metabolic panels, and liver function.

All test results will be reviewed by the principal investigator (or sub-investigators) to determine whether toxicity is developing in study subjects. Moreover, we will carry out cognitive tests every 3 months and volumetric MRI every 6 months (Table 1) to detect eventual brain toxicities. Finally, in case of AEs outside of the clinic, Study subjects will be provided contact information for both clinic and study coordinator.

The investigator or his designee is responsible for explaining the correct use of the investigational agents to the patient/caregiver/study partner, verifying that instructions are followed properly per drug manufacturer. Study staff will maintain accurate records of investigational product dispensing and collection and returning all unused medication to the Study Site at each in-person visit. Patients will be instructed to contact the investigator or the study coordinator as soon as possible if he or she has a complaint or problem with the investigational product so that the situation can be assessed.

If toxicities are identified, we will apply a special toxicity protocol. Per clinical trials, hepatotoxicity was primarily noted in controlled trials of Siponimod in patients. Notably, AST and ALT values were elevated above 3 times the upper limit of normal. If hepatotoxicity is noted, the subject will be withdrawn from the study and not replaced if this occurs after Visit 7. Please refer to the section, Procedure Used in Case of Toxicity.

PREPARATION/HANDLING/STORAGE/ACCOUNTABILITY

ACQUISITION AND ACCOUNTABILITY

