Manufacturer shelf-life is 18 months. We will be acquiring the study drug from Novartis in small batches over a period of 5 years. Study drug will be stored in a refrigerator (4°C) with excursions permitted to 2-10°C. The tablets should not be exposed to high temperature and humidity. Tablets should be protected from light. Temperature will be monitored and recorded to ensure the stability of study drug. Expiry dates will be monitored, and any expired products will be pulled from the active stock.

PREPARATION

Siponimod and matching placebo tablets of the same size and color to the active drug will be compounded by Novartis in accordance with GCP (IND #076122). The matching placebo will be of identical appearance to the study medication to maintain the double-blind design of the study.

MEASURES TO MINIMIZE BIAS: RANDOMIZATION AND BLINDING

This is a randomized, double-blind, placebo-controlled, parallel group study. The use of placebo is appropriate to minimize bias related to treatment expectations of the subject, study partner, and site investigator, as well as to changes in the relationship between the subject and study partners that might occur with the initiation of treatment and expectation of improvement in motoric symptoms or cognition. Changes in subject/study partner interactions can impact subject mood and might introduce biases that

cannot be quantified. The double-blind use of placebo will also prevent bias in the clinical and scientific assessments.

Randomization will be carried out by our study biostatistician and the medication or placebo prepared accordingly by our clinical pharmacist. This procedure was developed to ensure double blinding, i.e. neither the investigators, nor the study subjects will know the medication taken by study subjects until the completion of the study and the acquisition of all data.

Emergency unblinding for AEs will be performed by the unblinded pharmacy team if the subject's well-being requires knowledge of the subject's treatment assignment. The subject's treatment status will remain blinded to other study personnel and Principal Investigator.

The investigator should make every effort to contact the medical monitor prior to unblinding a subject's treatment assignment. If a subject's treatment assignment is unblinded, the medical monitor and DSMB must be notified immediately. All unblinding events will be recorded in the CRF.

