At the baseline visit (Visit 2), subjects who have met all the eligibility criteria for enrollment will be randomly assigned to one of two treatment groups:

1. Placebo (n=35) or
2. Siponimod 1 mg/day (n=70)

Randomization will be 2:1 and designed by our biostatistician. Randomization will take place during the Baseline visit.

In case of toxicity finding, the blinding will remain in effect as neither the Investigator, nor site staff will be informed whether the participants receive Siponimod or placebo. However, the study pharmacist will be informed in case there is need to adjust dosing if participants are treated with investigational product.

An independent statistician supporting the DSMB will be unblinded and may unblind the DSMB if required for proper study monitoring. All staff and research personnel involved in this study will remain blinded until all subjects have completed the trial and scientific data acquired.

STUDY INTERVENTION COMPLIANCE

Patient compliance with study medication will be assessed at each visit. Compliance will be assessed by direct questioning and counting returned tablets. Deviation(s) from the prescribed dosage regimen should be recorded in the CRF.

Patients who are significantly noncompliant will be instructed to discontinue medication from the study. A patient will be considered significantly noncompliant if he or she misses more than 21 consecutive days of study medication during the study without extenuating circumstance, for example: development of an SAE. Patients who stop dosing due to development of an SAE will have their case reviewed by investigator, site, medical monitor, DSMB, and Principal Investigator for prescribing appropriate actions. Similarly, a patient will be considered significantly noncompliant if he or she is judged by the investigator to have intentionally or repeatedly taken more than the prescribed amount of medication. Drug accountability will be emphasized at the start-up meeting, and drug accountability will be monitored throughout the study.

Temporary discontinuation of treatment with study drug due to ARIA-E should not be considered as non-compliance.

CONCOMITANT THERAPY

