terminations will also be indicated to the DSMB in a timely manner. The IRB will be notified per Barrow Neurological Institute IRB Policy regarding Adverse Events Reporting.

- Complaint Handling

The investigator or his/her designee is responsible for handling the following aspects of the product complaint process in accordance with the instructions provided for this study:

- recording a complete description of the product complaint reported and any associated AEs using the study-specific complaint forms provided for this purpose.
- informing the medical monitor within 24-48 business hours of subject complaints.

- Safety Measures

+ Routine Clinical Laboratory Tests

Routine hematology, blood chemistry will be performed at screening and subsequent follow-up visits as described in the schedule of events.

+ Electrocardiograms

For each subject, 12-lead digital electrocardiograms (EKGs) will be collected according to the Schedule of Events. The EKG at screening will be a single EKG and will be interpreted by the principal investigator, or sub-investigator. Every effort will be made to obtain EKGs around the same time of day; however, if unable to schedule for the same time, EKGs will still be completed per protocol. Patients must be supine for approximately 5 to 10 minutes before EKG collection

. EKGs will be interpreted by the principal investigator, or sub-investigator, with every effort made to have EKG results reviewed as close to time of collection as possible. Ideally EKG result review will be completed while the subject is still at site, so that any clinically relevant findings are identified with subject present.

After enrollment, if a clinically significant increase in the QT/corrected QT (QTc>500) interval from baseline, or other clinically significant quantitative or qualitative change from baseline, is present, the investigator will assess the subject for symptoms (for example, palpitations, near syncope, syncope) and to determine if the subject can continue in the study. The investigator, or qualified designee, is responsible for determining if any change in patient management is needed and must document their review of the EKG printed at the time of evaluation along with the final overread EKG and any alert reports.

+ Physical Examination

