A complete physical examination (with neurological exam) will be performed at the visits listed in the study protocol and schedule of events. An abbreviated physical examination, to include an ophthalmic examination and routine examination of the heart, lungs, abdomen, skin, and oral cavity, will also be performed. Sitting vital signs (blood pressure, heart rate, respiratory rate, and temperature), after each subject sits quietly for at least 5 minutes, and body weight will be assessed at the Screening Visit and at each subsequent visit.

+ Vital Signs

Body temperature (oral or tympanic) will be measured as specified in the Schedule of Activities and as clinically indicated.

Blood pressure and pulse rate (PR) will be measured as specified in the Schedule of Activities and as clinically indicated. Blood pressure and PR should be measured after at least 5 minutes of sitting.

+ Body Weight and Height

Body weight and height will be recorded as specified in the Schedule of Activities and as clinically indicated.

+ Neurological Examination

A directed neurological examination will be performed by the investigator at the time points specified in the protocol and schedule of events.

Any clinically significant change from baseline on follow-up physical/neurological examinations should be recorded as an AE and reported in the CRF. If additional ARIA-H, ARIA-E, are detected, an additional neurological exam may be performed by the investigator.

- Toxicity Assessment

During visits at the study site, we will collect blood samples and conduct blood counts and comprehensive metabolic panels to monitor hematologic and metabolic toxicities. All lab results will be reviewed by the primary investigator, or sub-investigators, to determine if any clinically significant findings are seen that could be attributed to Siponimod related toxicities.

- Procedure Used in Case of Toxicity

If toxicities are identified, we apply a special toxicity protocol. The hematologic or chemistry values indicative of severe AEs are those listed in exclusion criteria.

If toxicity, including cardiac SAEs, is suspected, or proven, to be linked to Siponimod, subjects will stop taking the study drug for 7 days, and undergo new blood tests after at least 7 days of washout. If test results continue showing toxicity, subjects will be withdrawn from the study and not replaced if this occurs after Visit 7.

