An Emergency Code Break procedure will be available to the investigator to allow for unblinding of a patient, i.e. informing the investigator to which treatment group the patient has been assigned. Such procedures should only be utilized in emergency situations when the identity of the subject must be known by the investigator in order to provide appropriate medical treatment, i.e. unblinding is not required and should not be performed if knowledge of the patient's treatment group would have no influence on how the patient is being treated in the emergency situation.

EXPECTEDNESS

The Principal Investigator will be responsible for determining whether an adverse event (AE) is expected or unexpected. An AE will be considered unexpected if the nature, severity, or frequency of the event is not consistent with the risk information previously described for the study intervention.

TIME PERIOD AND FREQUENCY FOR EVENT ASSESSMENT AND FOLLOW-UP

The occurrence of an adverse event (AE) or serious adverse event (SAE) may come to the attention of study personnel during study visits and interviews of a study participant presenting for medical care, or upon review by a study monitor.

All AEs including local and systemic reactions not meeting the criteria for SAEs will be captured on the appropriate case report form (CRF). Information to be collected includes event description, time of onset, clinician's assessment of severity, relationship to study product (assessed only by those with the training and authority to make a diagnosis), and time of resolution/stabilization of the event. All AEs occurring while on study must be documented appropriately regardless of relationship. All AEs will be followed to adequate resolution.

Any medical condition that is present at the time that the participant is screened will be considered as baseline and not reported as an AE. However, if the study participant's condition deteriorates at any time during the study, it will be recorded as an AE.

Changes in the severity of an AE will be documented to allow an assessment of the duration of the event at each level of severity to be performed. AEs characterized as intermittent require documentation of onset and duration of each episode.

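### The emergency unblinding rule in section 8 keeps the arm from the Principal Investigator, while the code-break rule in section 11 gives it to the investigator who must treat

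*Protocol*

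**What the plan says.** The protocol deals with emergency unblinding in two places.

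- **Section 8, Measures to Minimize Bias: Randomization and Blinding.** The unblinded pharmacy team breaks the code for an adverse event if the subject's well-being requires the arm to be known. The next sentence says the "treatment status will remain blinded to other study personnel and Principal Investigator". The paragraph after it adds: "The investigator should make every effort to contact the medical monitor prior to unblinding". No recipient of the information is named.
- **Section 11, under Relationship to Study Intervention.** An Emergency Code Break is available to the investigator for "unblinding of a patient, i.e. informing the investigator to which treatment group the patient has been assigned". It is reserved for "emergency situations when the identity of the subject must be known by the investigator in order to provide appropriate medical treatment", and is barred where knowing the arm would not change treatment.

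Section 8 also contains two general blinding sentences with no emergency exception. One says that neither investigators nor subjects learn the treatment before the study and data collection are complete. The other keeps all staff and research personnel blinded until every subject has finished. On a toxicity finding, a further sentence says that "neither the Investigator, nor site staff will be informed whether the participants receive Siponimod or placebo", with only the study pharmacist told in case dosing needs adjusting.

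**The concern.** Both rules are triggered by patient need, but they differ on who may be told. Section 11 exists so that the investigator can treat. Section 8, read literally, keeps the arm from the Principal Investigator in the very case where it says the subject's well-being requires that the arm be known. A site holding both instructions has to settle the difference during an emergency.

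The setting makes this more than a drafting curiosity. Safety is the primary objective, and siponimod can slow the heart. The first dose at each strength is given in clinic under six hours of observation. Section 1.1 (Visit 2) treats a heart rate below 55 after the first dose as calling for immediate intervention by the investigator.

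**Working it through.** No arithmetic applies. The check is whether any reading of the text lets both rules be followed.

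**1. Same event?** Yes. Section 8 acts when the subject's well-being requires the arm to be known. Section 11 acts in "emergency situations when the identity of the subject must be known by the investigator in order to provide appropriate medical treatment". Neither section presents itself as an exception to the other.

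**2. Who is told?**

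| Treating clinician | Section 8 | Section 11 |
|---|---|---|
| Principal Investigator | stays blinded, by name | told, as the investigator |
| Sub-investigator | stays blinded if the phrase about other personnel means everyone outside the pharmacy team; may be told if it means only those not involved in the break | told, if acting as the investigator |
| Physician outside the study | not addressed, so not barred | not addressed |

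The first row is a conflict on every reading. The second depends on what the word *other* refers to. The pharmacy team is the only group named just before, so the wider meaning is the more natural one, but the text does not settle it.

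**3. Can the first row occur?** Yes. The Synopsis describes a single-site trial. Section 8 (Dosing and Administration) says: "All test results will be reviewed by the principal investigator (or sub-investigators) to determine whether toxicity is developing in study subjects". Section 10 (Electrocardiograms) says: "EKGs will be interpreted by the principal investigator, or sub-investigator". The Principal Investigator is therefore one of the physicians who may be managing an acute event.

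**4. Does other text resolve it?** No. The two general blinding sentences in section 8 make no mention of the code break, so they too disagree with section 11. The instruction that "The investigator should make every effort to contact the medical monitor prior to unblinding" suggests that the investigator starts the process, but it does not say the investigator receives the answer.

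**5. How far does it reach?** Routine toxicity handling in section 10 is to stop for 7 days, retest, then resume at a dose 0.25 mg lower or withdraw. None of that needs the arm. Section 11 also forbids breaks that would not alter care. What remains is the rare emergency in which the arm does alter care.

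**The case against.** The best counter-argument is that the protocol uses *investigator* and *Principal Investigator* as separate roles. Section 8 (Study Intervention Compliance) lists both among those who review a subject who stops dosing because of a serious adverse event. The emergency paragraphs of section 8 also use both terms close together. On that view a treating sub-investigator may be told while the Principal Investigator stays blind, and sub-investigators are available for safety review. Having the pharmacy hold the code also protects later causality ratings. This narrows the conflict and may remove it for sub-investigators. It does not remove it for a treating Principal Investigator, because section 11 makes no such exclusion and the protocol's use of the two terms is not consistent.

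Three stronger readings are tempting, and the documents do not support them.

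- **A reader might take the section 8 toxicity sentence ("neither the Investigator, nor site staff will be informed whether the participants receive Siponimod or placebo") as a second, independent ban on emergency disclosure**, particularly since section 10 says "If toxicity, including cardiac SAEs, is suspected, or proven, to be linked to Siponimod" and so counts cardiac events as toxicity. The sentence that follows it in section 8 is about the pharmacist adjusting the dose, so it most naturally concerns dose changes. It should be aligned, but it is not separate evidence.
- **A reader might infer that section 8 leaves no treating physician able to learn the arm.** It restricts study personnel and the Principal Investigator. It does not bar telling an emergency or hospital physician outside the study.
- **A reader might infer that the trial's results are at risk.** Nothing in the sample size, alpha or planned analyses depends on this rule.

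Section 13 (Key Roles and Study Governance) promises a Manual of Operations setting out roles. It may name a recipient, so the absence of one in section 8 carries little weight by itself. A manual does not cure a contradiction within the protocol.

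**Conclusion.** The conflict is real and should be corrected, as a minor patient-safety and consistency point. It is certain when the Principal Investigator is treating. It extends to a sub-investigator only if the section 8 phrase means everyone outside the pharmacy team.

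Its size cannot be calculated, because the protocol gives no code-break rate. Code breaks are assumed to be rare, and the problem is limited to those in which knowing the arm changes treatment. The enrolment of 105 (70 siponimod, 35 placebo), the significance level and the analyses are unaffected. The conclusion also assumes that the Principal Investigator may personally manage an emergency, which the protocol permits but does not require.

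**What to change.** Make section 11 the governing rule and bring section 8 into line with it.

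1. In section 8, replace the sentence on who remains blinded after emergency unblinding with: *The unblinded pharmacy team will disclose the assignment only to the clinician treating the emergency who needs it for care (a study investigator, including the Principal Investigator if treating, or a non-study physician), after an attempt to reach the medical monitor where possible; all other study personnel remain blinded.* Naming the outside physician matters: a rule limited to study investigators would be narrower than the present text.
2. Add *except under the Emergency Code Break procedure* to three section 8 sentences: the one on investigators and subjects not knowing the treatment until completion, the one on all staff and research personnel staying blinded, and the toxicity sentence.
3. Keep the existing requirement to notify the medical monitor and DSMB and to record every break in the CRF.

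The cost is one replaced sentence and one clause added in three places, with the IRB approval that any amendment needs. At most one more clinician per code break knows the arm, which section 11 already intends. No change to who rates causality is needed to resolve the contradiction.

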9. STUDY INTERVENTION DISCONTINUATION AND PARTICIPANT DISCONTINUATION/WITHDRAWAL

DISCONTINUATION OF STUDY INTERVENTION

A subject may discontinue study drug under any of the following circumstances:

- The subject wishes to discontinue study drug treatment for any reason.
- The subject experiences AEs that necessitate discontinuing study drug treatment. The Principal Investigator, medical monitor, and DSMB should be notified immediately.
- The investigator or DSMB decides to discontinue treatment for medical reasons. The reason for termination of study drug before study completion should be recorded in the CRF. At the time of study drug discontinuation, the End of Study Drug Visit should be administered. If the subject is not willing or able to return for all remaining study visits, they should be asked to return for the Week 52 and Week 78 visits, as well as returning all unused study drug. If this is not possible, they should be contacted by phone at Week 52 for the End of Study assessments (adverse events, and concomitant medications). The reason for withdrawal should be recorded in the case report form (CRF). The subject should complete the procedures for the Early Termination Visit, provided written consent to do so has not been withdrawn.

Subjects who discontinue or are withdrawn from the study following randomization:

- if they stop treatment (drug or placebo) before Visit 7, they will be replaced by new subjects
- if they stop treatment (drug or placebo) after Visit 7, they will not be replaced.

LOST TO FOLLOW-UP

To be considered lost to follow up, the study coordinator will make three documented attempts to contact the subject, who must also miss two scheduled visits. If these efforts are unsuccessful, a certified letter will be sent to the subject. If no response is received after this communication, then, the subject will be officially considered lost to follow up.

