Description of Study Intervention:	Siponimod 1 mg/day vs. placebo taken daily orally (ratio 2:1 drug: placebo). The drug escalation scale will be used starting from 0.25mg/daily ending with final dosage of 1mg/day.
Study Duration:	The trial will last 4-5 years.
Participant Duration:	Participants completing the study will be involved for up to 20 months in duration, from screening to end of study. Treatment period will be 52 weeks and 6-month washout/observation

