- Blood biomarkers
- Dispense study drug and drug diary
- Drug accountability
- Adverse event assessment

Visit 13 at Day 364 End of Study Drug Treatment (\pm 7 days)

The following tests and procedures will be completed in clinic:

- Concomitant medication reconciliation
- Drug accountability and drug diary
- Coagulation panel labs (PT, PTT, INR) to be completed pre-optional lumbar puncture (LP).
- Labs (CBC w/ diff, CMP, TSH)
- EKG
- Vital signs including weight
- Neuro and physical exam
- Blood biomarkers
- OCT Eye Exam
- Volumetric MRI (+4 weeks)
- Cognitive Assessments (MMSE, ADAS-Cog13, CDR-SOB, ADCS-ADL)
- Drug accountability and collect drug diary
- Adverse event assessment

The following are to be completed if participants opted into one, or both, of the optional studies:

- *Lumbar puncture (to measure CSF biomarkers) followed by phone check in 24hrs post-lumbar puncture*
- *Saliva collection*

Visit 14 at Day 392 (\pm 7 days)

The following tests and procedures will be completed in clinic:

- Concomitant medication reconciliation
- Labs (CBC w/ diff, CMP, TSH)
- EKG
- Vital signs including weight
- Neuro and physical exam
- Blood biomarkers
- Adverse event assessment

The following are to be completed if participants opted for the Saliva sub-study:

- *Saliva collection*

End of Study at Day 546 (\pm 7 days)

The following tests and procedures will be completed in clinic:

- Concomitant medication reconciliation
- Labs (CBC w/ diff, CMP, TSH)
- EKG
- Vital signs including weight
- Neuro and physical exam
- Volumetric MRI (\pm 4 weeks, patients can come before or after visit for end of study)
- OCT Eye exam
- Blood biomarkers
- Cognitive assessments (MMSE, ADAS-Cog 13, CDR-SOB, ADCS-ADL)
- Adverse event assessment

The following are to be completed if participants opted Saliva sub-study:

- *Saliva collection*

Unscheduled Visits

Unscheduled visits will be at the investigator's discretion. All unscheduled visits will include the following tests and procedures:

- EKG
- Vital Signs and Weight
- Neurological and Physical Exam
- Labs (CBC with differential, CMP, TSH)
- Blood Biomarkers
- Medication reconciliation
- Adverse Event Assessment
- OCT Eye exam (in the case of blurred vision or other ocular issues)

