4. OBJECTIVES AND ENDPOINTS

OBJECTIVES	ENDPOINTS
PRIMARY	
The primary objective of the study is to assess the safety and tolerability of Siponimod in mild AD dementia subjects.	Safety will be assessed at each study visit through completion of comprehensive tests and procedures aimed at monitoring for potential adverse events (AEs). Study staff will also gather direct reports from subjects regarding any adverse events.
SECONDARY	
The secondary objective of the study is to assess the effects of Siponimod on AD-associated neurodegeneration by deriving annual brain atrophy rates from volumetric MRI (vMRI).	Siponimod was observed to slow rates of brain atrophy in both RRMS and SPMS patients. Thus, the aim is to assess the medical benefits of the drug in mild AD dementia subjects by assessing whether brain atrophy slows with Siponimod treatment. Subjects will undergo volumetric MRI (vMRI) measurements of the hippocampus, cortical thickness, and global thickness as indicators of neurodegeneration.
TERTIARY	
The tertiary objective of study is to assess the effects of Siponimod on cognition following administration of study drug vs. placebo.	Cognition will be assessed by comparing the changes in two assessments: ADCS-ADL and ADCOMS from baseline to various visit timepoints, including Week 78 (End of Study).
EXPLORATORY	
Exploratory objectives will include:	
i) measurements of markers found in the CSF fluid that are known to be associated with mild AD dementia and inflammation before and after treatment	i) CSF biomarkers that will be assessed include amyloid beta 40 & 42, Tau, and Phospho-Tau.
ii) assessment of blood inflammatory markers before and after treatment	ii) Blood inflammatory markers include CRP, TNF- α , IL-1 β , IL-6, IL-8, and IL-10 (54-plex measured on the Meso Scale Discovery [MSD] ELISA platform). Plus, we will count the number of white blood cells (B and T lymphocytes, macrophages, etc) in the blood to estimate the impact of Siponimod on peripheral markers of the immune system.
iii) to assess levels of A β found in saliva samples collected before and after treatment with Siponimod vs. placebo	iii) Saliva markers that will be assessed are A β 40 and A β 2. Saliva A β levels is a recent biomarker that has been identified to study AD. Thus, we propose to explore the effects of Siponimod on A β 40 and A β 2 throughout the course of the study.

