If toxicity markers improve, subjects will resume dosing at the prior lower dose (i.e., toxic dose minus 0.25 mg) and remain on this regimen until the end of the study. In case of a second toxic event, dosing will again be stopped for 7 days, and blood tests conducted. If the test results continue showing toxicity, subjects will be withdrawn and not replaced if this occurs after Visit 7. If toxicity markers improve, subjects will resume dosing at the previous lower dose (i.e., toxic dose minus 0.25 mg) and remain at this lower dose until the end of the study.

In case of a third toxic event, subjects will be withdrawn and not replaced if this occurs after Visit 7. When study medication is withdrawn, study subjects will be recorded as “End Of Study Drug Visit” and undergo the corresponding assessments (Week 52 in Table 1). Then, the subjects will be asked to complete the corresponding washout period schedule of assessments: (Week 56 in Table 1) and 26 week “End of Study” (Week 78 in Table 1).

- Tolerability Assessment

Tolerability of Siponimod in study subjects will be derived from the frequency of AEs and study withdrawal motivated by subjects’ discomfort during the dosing period.

- Standard MRI (screening 1)

Patients who do not have an MRI scan within the past 12 months of Screening Visit Day 1 will be scheduled for an vMRI or CT during the screening period with results obtained before randomization is decided. (MRI is preferred).

>> Routine MRI Scan (default choice)

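### The last-resort phone contact for early stoppers is set at Week 52 but labelled End of Study, which is Week 78 elsewhere; read literally, scheduled adverse-event ascertainment for them stops 26 weeks early

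*Protocol*

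**What the plan says.** Protocol section 9 (Discontinuation of Study Intervention) sets out steps for a subject who stops study drug. The End of Study Drug Visit is done when the drug is stopped. A subject who will not or cannot attend all remaining visits comes next: "they should be asked to return for the Week 52 and Week 78 visits, as well as returning all unused study drug". If that too is impossible, "they should be contacted by phone at Week 52 for the End of Study assessments (adverse events, and concomitant medications"). The same paragraph adds: "The subject should complete the procedures for the Early Termination Visit", provided consent for this has not been withdrawn.

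The rest of the protocol keeps two milestones apart:

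- Section 1.1 lists "Visit 13 at Day 364 End of Study Drug Treatment" and, separately, "End of Study at Day 546".
- The tertiary endpoint in section 4 runs to several visits, "including Week 78 (End of Study").
- The synopsis gives the overall plan: "Treatment period will be 52 weeks and 6-month washout/observation".
- Table 1 schedules AE assessment at Weeks 52, 56 and 78.
- Section 10 (Procedure Used in Case of Toxicity) asks subjects whose medication is withdrawn to complete the washout assessments, "Week 56 in Table 1) and 26 week “End of Study” (Week 78 in Table 1"), and gives no phone alternative.

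**The concern.** The fallback attaches the Week 78 label to a Week 52 contact. It also replaces two requested contacts with one, although the sentence before it shows that both time points were wanted. Site staff who follow the text literally will make one call at Week 52 and schedule nothing at Week 78.

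Safety and tolerability are the primary objective, and reported AEs lead the primary endpoint. Section 12 (Safety Analyses) defines a treatment-emergent AE as one that begins or worsens once study drug has been given. It sets no closing date and tabulates subject incidence by treatment received. On that definition, new events up to Week 78 count for subjects who are asked about them, while phone-only stoppers are not asked after Week 52. An analysis plan could set a common window, but it could not recover events nobody asked about.

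The Early Termination Visit is a smaller matter: the name appears in neither the visit list in section 1.1 nor Table 1. Section 9 already requires the End of Study Drug Visit at stopping, so it is unclear whether a second visit is meant or which procedures it would contain.

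**Working it through.** **Inputs.** End of Study Drug is Day 364 and End of Study is Day 546 (section 1.1 and Table 1). The fallback call is at Week 52 (section 9). Section 10 gives the interval to End of Study as 26 weeks.

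**Reproducing the plan's own interval.** 364 / 7 = 52 weeks and 546 / 7 = 78 weeks. The difference is 546 - 364 = 182 days, and 182 / 7 = 26 weeks. This agrees with the 26 weeks in section 10.

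**Calendar loss under the literal reading.** It is 182 / 546 = 33% of the study period. It is the same 26 weeks whenever the subject stops, because the call is fixed at Week 52.

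**Observation after the last dose.** For a stop at week s, observation is 52 - s weeks to the call and would be 78 - s weeks to End of Study. A completer has 78 - 52 = 26 weeks.

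| Stop at week | To the Week 52 call | To Week 78 | Completer |
|---|---|---|---|
| 10 | 42 | 68 | 26 |
| 26 | 26 | 52 | 26 |
| 40 | 12 | 38 | 26 |
| 48 | 4 | 30 | 26 |

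The two clocks give different answers. By calendar time every phone-only subject loses 26 weeks. By time since last dose, 52 - s is below 26 only when s is above 26, so only stops after Week 26 are observed for less time than a completer.

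**Comparator.** The comparison is with subjects followed to Week 78. If the 26-week visit in section 10 is counted from drug withdrawal, a toxicity withdrawal at Week 10 would end at 10 + 26 = Week 36, also before Week 78. Sections 9 and 10 do not settle this between them.

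**The case against.** The strongest reply is that the sentence probably contains a simple slip. If the label is right and the week is wrong, the call belongs at Week 78 and the tail of follow-up is not lost. The documents do not show which was meant. This stands as a reason to state the loss only for the literal reading. It does not remove the need for an edit, because on either reading one contact replaces two and the text disagrees with Table 1.

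The second reply is that little of the primary assessment is touched. The synopsis ties the primary objectives to evaluations during the dosing period, and section 10 derives tolerability from that period. A Week 52 call spans it. This largely stands: what is lost lies mainly in the washout. AEs are nonetheless scheduled for collection there, and the incidence table does not exclude them.

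A reader might infer more than the documents support:

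- **That AE follow-up ends at Week 52.** Section 11 has recorded AEs followed to resolution and keeps possibly related serious events reportable after participation. Only scheduled asking about new events stops.
- **That late drug effects are under-counted where they matter most, in subjects mostly on drug who stopped for toxicity.** Section 9 covers stopping for any reason and gives no stop rates by arm. The 2:1 allocation alone does not show who ends up phone-only. Early stoppers have more time off drug before the call than completers have before End of Study.
- **That a Week 10 stopper goes 42 weeks without contact.** This subject has a visit at stopping, and section 9 does not cancel the routine phone visits, which run to Day 308. The text is silent, so no gap of that length is established.
- **That about 10 subjects are affected.** The roughly 10% attrition in section 12 is an all-cause sample-size allowance. Phone-only subjects are an unknown subset, and those who stop before Visit 7 are replaced.

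**Conclusion.** The inconsistency is real: section 9 disagrees with sections 1.1, 4 and 10 and with Table 1 about what Week 52 is. Taken literally, subjects on the last-resort fallback have no scheduled AE ascertainment in the final 26 weeks, and the open-ended incidence table would combine unequal observation periods. The size per subject is 182 of 546 days. The number of subjects is unknown and probably small, since the fallback applies only after two fuller options have failed.

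This rests on two assumptions: that the call is made at Week 52 as written, and that comparison subjects are followed to Week 78. The documents do not establish a bias of known direction or size between the arms. The point is minor, but it is more than a label correction because it decides whether a data-collection contact exists. The undefined Early Termination Visit is purely editorial.

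**What to change.** Reconcile section 9 with the toxicity procedure in section 10 and with Table 1, using End of Study Drug for Week 52 and End of Study for Week 78 throughout. Reword the fallback so that subjects who cannot attend are phoned for AEs and concomitant medications at both weeks. Scheduled ascertainment for them would then run to Week 78, restoring 26 of 78 weeks.

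Replace the Early Termination Visit with the End of Study Drug Visit that section 9 already requires, or delete the sentence.

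The cost is one extra phone call for a few subjects and a short edit to section 9, with no new procedure or staff.
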